#### 7.2.1.2.1 *Serious Adverse Event*

International Conference on Harmonization (ICH) Guidelines and federal regulations define a serious adverse event (SAE) as any untoward medical occurrence that at any dose:

- Results in death;
- Is life-threatening. This means that the patient is at risk of death at the time of the event; it does not mean that the event hypothetically might have caused death if it were more severe;
- Requires or prolongs patient hospitalization;
- Results in persistent or significant disability or incapacity; or

- Is a congenital anomaly or birth defect.

Important medical events that may not be immediately life-threatening or result in death or hospitalization but that may jeopardize the patient or require intervention to prevent one of the above outcomes usually should also be considered serious.

#### 7.2.1.2.2 Severity

The severity of each AE must be assessed and recorded on the Adverse Events page of the EDC as mild, moderate, or severe.

- Mild: An AE that does not interfere with usual activities;
- Moderate: An AE that interferes with usual activities; or
- Severe: An AE that is intense or debilitating and interferes with usual activities.

#### 7.2.1.2.3 Relationship to Study Medication

The relationship of each AE to study medication must be assessed and recorded on the Adverse Events page of the EDC as one of the following:

- Not related;
- Possibly related; or
- Probably or definitely related.

#### 7.2.1.3 Recording Adverse Events

All AEs that occur during the study must be recorded in the Adverse Events page of the EDC. All Adverse Event EDC entries should contain a brief description of the event, date and time of onset, duration, intensity, treatment required, relationship to study medication, action taken with regard to study medication, outcome, and whether the event is classified as serious.

#### 7.2.1.4 Reporting Serious Adverse Events

The Investigator must report any SAE that occurs during the study (i.e., between study entry and Visit 4), regardless of relationship to study medication, to [REDACTED] [REDACTED] within 24 hours of discovering the event. In addition, if the investigator learns of an SAE occurring after the last follow-up visit, but within 30 days after the last administration of the study drug, he/she should immediately report the event to the Safety Officer at [REDACTED].

Directions for reporting an SAE appear below.

**SERIOUS ADVERSE EVENT REPORTING INSTRUCTIONS**  
[REDACTED] **INTERNATIONAL**  
**Clinical Trials Safety Center**

Email for Reporting SAEs: [REDACTED]

Fax: [REDACTED]

Telephone: [REDACTED] (for urgent issues/questions during business hours)

1. Fax or email the SAE report form and any supporting documentation to the Safety Center within 24 hours of becoming aware of the event.
2. Telephone the Safety Center if you have an urgent issue or cannot fax or email the SAE report form. Provide the Safety Center personnel with the Investigator's name, your name, the telephone number where you can be reached, your study site number, the protocol number and title, and the patient number for an urgent concern/issue.
3. Provide the Safety Center personnel with the Investigator's name, your name, the telephone number where you can be reached, your study site number, the protocol number and title, and the patient number.

The Investigator and the Sponsor (or Sponsor's designee) will review each SAE report and evaluate the relationship of the SAE to study medication. Based on the Investigator's and Sponsor's assessment of the SAE, a decision will be made concerning the need for further action. The primary consideration governing further action is whether new findings affect the safety of patients participating in the clinical study. If the discovery of a new SAE related to the study medication raises concern over the safety of continued administration of the study medication to patients, the Sponsor (or Sponsor's designee) will take immediate steps to notify the FDA/other regulatory authority and all Investigators participating in clinical studies of the study medication.

Further action that may be required includes the following:

- Modification of the protocol, including the addition of investigators;
- Discontinuation or suspension of the study;
- Modification of the existing consent form and informing current study participants of new findings; or
- Addition of any newly identified study medication-related AEs to the list of expected AEs.

#### *7.2.1.5 Follow-Up of Adverse Events*

The Investigator must continue to follow all SAEs and those non-serious events assessed as possibly, probably, or definitely related to the study medication until they resolve or until the Investigator assesses them as chronic or stable. The follow-up information must be reported to the Sponsor. This follow-up may extend after the end of the study.

#### *7.2.1.6 Reporting Safety Information*

The Investigator must promptly report to his or her Institutional Review Board (IRB) or Independent Ethics Committee (IEC) all unanticipated problems involving risks to patients. This includes death from any cause and all SAEs assessed as possibly, probably, or definitely related to the study medication, and any other events required to be reported by the IRB/IEC.

#### *7.2.1.7 Protocol Deviations Due to an Emergency or Adverse Event*

In the case of an emergency or AE, departures from the protocol may be necessary. Such protocol deviations will be determined as allowable on a case-by-case basis. The Investigator or other physician in attendance in such an emergency must contact the Medical Monitor as soon as possible to discuss the circumstances of the emergency. The Medical Monitor and the Investigator will confer to decide whether the patient should continue to receive study medication. All protocol deviations and the reasons for such deviations must be noted in the EDC.

### **7.2.2 *Physical Examination***

Physical examinations will be performed at Visit 1. A directed examination of the ears (external inspection, examination of the external auditory canal, and otoscopic visualization of the tympanic membrane), head, nose and oropharynx will be performed.

Vital signs (temperature, blood pressure, and pulse) will be assessed at Visits 1, 3 & 4.

### **7.2.3 *Pregnancy Test***

A urine pregnancy test will be performed at Visit 1 for female patients of childbearing potential (females who have had menarche and are not premenstrual, not postmenopausal or not surgically sterile). This test will be performed at the study site or at the local laboratory used by the site. A negative result is required before the patient can be randomized.

Moreover, females must have agreed to use adequate birth control methods to prevent pregnancy throughout the study. Adequate birth control methods included topical, hormonal-oral, implantable or injectable contraceptives; mechanical-spermicide in conjunction with a barrier such as condom or diaphragm; intrauterine device (IUD); or surgical sterilization of partner (must be  $\geq$  6 months post vasectomy). For non-sexually active females, abstinence was regarded as an adequate method of birth control; however, if the patient became sexually active during the study, she must have agreed to use adequate birth control methods as defined above for the remainder of the study.

## **8. STUDY CONDUCT**

### **8.1 Schedule of Observations**

A schedule of observations and assessments to be performed during the study is provided in Table 1.

**Table 1 Schedule of Observations**

Evaluation	Visit 1 Screening/ Study Entry	Visit 2 By Telephone	Visit 3 End of Treatment	Visit 4 Post- Treatment Follow-Up
Study Day	1	3-4	8-10 or within 2 days of early termination	15-17
Informed Consent (and Assent Form when applicable)	X			
Inclusion/exclusion criteria	X			
Medical history	X			
Concurrent symptoms/conditions	X			
Urine pregnancy test a	X			
Physical examination	X			
Vital signs b	X		X	X
Brighton grading	X		X	X
Ear pain	X		X	X
Edema	X		X	X
Ototorrhea	X		X	X
Overall Clinical Outcome			X	X
Microbiological culture of ear discharge c	X		X	X
Register patient visit through IWRS	X	X	X	X
Randomization through IWRS	X			
Dispense study medication and explain its use	X	X d		
Collect used and unused study medication containers			X e	
Dispense patient diary and explain its use	X			
Inquire about otitis symptoms		X f		
Review patient diary			X	X
Concomitant medications	X	X	X	X
Adverse events	X	X	X	X

a For female patients of childbearing potential.

b To include temperature, blood pressure, and pulse rate.

c If no discharge is present, no attempt to culture will be made.

d If patient with unilateral AOE at baseline becomes bilateral prior to Visit 3 a resupply study medication kit (with the same medication) will be dispensede. If patients forget to bring in containers at Visit 3, they must bring them in no later than Visit 4.

e If patients report no improvement in otitis symptoms, they will be asked to come in for a visit as soon as possible. At this visit, they may prematurely discontinue study treatment (in which case the visit will be recorded as Visit 3, the End of Treatment visit) or continue study treatment (in which case the visit will be recorded as an unscheduled visit).

## 8.2 Observations by Visit

### 8.2.1 Visit 1

Patients who may be eligible to participate in the study will be offered the opportunity to participate. The study will be explained to them and questions about the study will be answered. Patients who elect to participate will sign the Informed Consent Form (or have it signed by their legally authorized representative), and patients who are below the age of majority but able to give assent will sign the Assent Form, before any study procedures may be performed. The IWRS will assign a patient number, which will be used to identify the patient during screening and, if applicable, throughout the duration of the study. Patients who do not meet the inclusion and exclusion criteria will be registered as screen failures through the IWRS. Patients who have provided consent and met the inclusion and exclusion criteria will be enrolled and randomized through the IWRS.

Medical history, concurrent symptoms and conditions, and concomitant medications will be recorded, and a physical examination (as described in Section 7.2.2) will be performed. Female patients of childbearing potential will have a urine pregnancy test.

Brighton grading, otalgia, edema, and otorrhea will be evaluated as described in Appendix 2, and Sections 7.1.1.1, 7.1.1.3, and 7.1.1.4. A microbiological culture of ear discharge will be taken as described in Section 7.1.2 prior to the debridement.

The patient or caregiver will be given a medication kit containing a 7-day supply of study medication. The blind will be maintained as described in Section 6.4. A member of the study staff will instruct the patient or caregiver on how to open the vials and administer study medication, and will supervise the patient or caregiver during administration of first dose.

The patient or caregiver will be provided with a patient diary and be trained on its use. A member of the study staff will instruct the patient or caregiver in how to fill out the patient diary.

Patients will be instructed to refrain from swimming during the study treatment period and preferably until the final study visit is completed. Patients will also be advised to use a shower cap or neoprene head band when bathing.

If any AEs occur during Visit 1, they will be recorded in the Adverse Events page of the EDC.

### 8.2.2 Visit 2 (Phone Visit)

A study staff member will telephone each patient or caregiver on Day 3 or Day 4 of treatment. The information obtained at this “phone visit” will be recorded in the Visit 2 page of the EDC. Study staff will ask about and record any AEs and any changes in concomitant medications since Visit 1. Study staff will also ask about study medication compliance. Patients or caregivers will also be asked if otitis symptoms are improving or worsening. A specific questionnaire to obtain all these information will be used.

Patients who report no improvement in otitis symptoms will be asked to come in for an unscheduled visit as soon as possible. At this visit, the Investigator will choose one of the two following options for the patient:

1. Continue the patient in the study. The present visit will be recorded as an unscheduled visit. The patient should continue taking study medication without interruption. A debridement of the ear and placement of otowick may be needed.
2. Discontinue study medication. The present visit will be recorded as Visit 3, the End of Treatment visit. The patient will be withdrawn from the study and may be treated with other medication (standard treatment) as appropriate at investigator's discretion. The clinical outcome for the patient will be recorded as Treatment Failure.

If a patient has unilateral AOE at baseline, but develops AOE of the contralateral ear subsequently during the study, then at Visit 2 or at unscheduled visit prior to Visit 3, the investigator or designee will obtain a second kit number (with the same medication) through the IWRs to treat the contralateral ear. This information will be included in the Comments page and Resupply or replacement page of the EDC, and will not be considered as an AE.

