### **5.3 Withdrawal, Premature Discontinuation of Study Medication, and Replacement of Patients**

Patients must be withdrawn from the study if they withdraw consent to participate. Such withdrawal may occur at any time during the study. Patients are not required to state their reasons for withdrawing consent.

Patients who do not experience improvement in symptoms may prematurely discontinue treatment with study medication. This protocol includes an assessment of whether a patient who experiences no improvement at Visit 2 should discontinue study treatment, as described in Section 8.2.2. However, a patient may discontinue study treatment at the Investigator's discretion at any time during the study treatment period.

Patients may be required to discontinue study treatment after discussion with the Sponsor and/or Investigator for any of the following reasons:

- Adverse event(s);
- At the discretion of the Investigator;
- Violation of eligibility criteria; or
- Deviation from the treatment plan specified in the protocol (e.g., incorrect administration of study medication, failure to attend study visits).

In all cases, the reasons for premature discontinuation of study medication must be recorded in the Electronic Data Capture (EDC) and in the patient's medical records. If there is more than one reason for premature discontinuation of study medication, one reason will be listed in the EDC as the primary reason.

If possible, each patient who prematurely discontinues study treatment should report to the study site for an End of Treatment visit (Visit 3), as described in Section 8.2.3.

Patients who withdraw consent or discontinue study medication prematurely will not be replaced.

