### 6.7.1 Prohibited Concomitant Medications

The following medications will be prohibited during the study (unless the patient has prematurely discontinued study treatment):

- Any investigational drug;
- Any topical or systemic therapy for treatment of otitis externa or otitis media;
- Any systemic antifungal drug;
- Any antibiotic drug other than study medication;
- Any systemic corticosteroid, except nasal or inhaled corticosteroids at stable doses (at least 30 days prior to enrollment)
- Any systemic drug (prescription or over the counter) with anti-inflammatory properties (including biologic response modifiers, nonsteroidal anti-inflammatory drugs such as ibuprofen, naproxen, and cyclooxygenase-2 inhibitors); acetylsalicylic acid for cardiovascular prevention at doses of 325mg per day or less is allowed
- Any compound, agent or substance that is applied to the evaluable external ear or instilled in the evaluable ear canal, other than study medication.

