### 7.2.1 *Adverse Events*

#### 7.2.1.1 *Definitions*

An adverse event (AE) is any untoward medical event that occurs in a patient or subject who has received an investigational product, and does not necessarily have a causal relationship with this treatment. An AE can therefore be any unfavorable and unintended sign (including abnormal laboratory finding), symptom, or disease temporally associated with the use of an investigational product, whether or not related to the product.

An illness present at entry to the study is considered a pre-existing condition and will not be considered an AE. However, if a pre-existing condition worsens during the study, this may be considered an AE. Pre-existing conditions will be documented in the EDC. If pre-existing signs and symptoms of AOE (otalgia, edema and otorrhea) worsen during the study, this will be considered a treatment failure instead of an AE. If a patient has unilateral AOE at baseline and it becomes bilateral during the study, then the AOE in the contralateral ear will not be considered as an adverse event. All AEs, including intercurrent illnesses, that occur during the study (i.e., between study enrollment and Visit 4) must be reported and documented as described below.

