#### **8.2.4      Visit 4**

Visit 4 will take place between Day 15 and Day 17. All patients (except those who have been withdrawn from the study or have withdrawn their consent as described in Section 5.3) are expected to attend Visit 4 (TOC).

Adverse events and concomitant medications will be recorded, and vital signs will be assessed.

Brighton grading, otalgia, edema, and otorrhea will be evaluated as described in Appendix 2, Sections 7.1.1.1, 7.1.1.2, 7.1.1.3, and 7.1.1.4. Overall Clinical Outcome will be evaluated

by the Investigator as described in Section 7.1.1.5. A microbiological culture of ear discharge (if discharge is present) will be taken as described in Section 7.1.2.

If patient took rescue medication (see Section 6.7.2) prior to this visit, the ear discharge will not be collected, because patient will be considered Treatment Failure.

Upon completing Visit 4, the patient will have completed his or her participation in the study.

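### Patients taken off study medication for no improvement are withdrawn and excepted from Visit 4, so scheduled safety assessment ends early according to outcome, and the protocol contradicts itself on their status

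*Protocol*

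**What the plan says.** Protocol 8.2.2 sets the sequence. "A study staff member will telephone each patient or caregiver on Day 3 or Day 4 of treatment". Patients who report no improvement "will be asked to come in for an unscheduled visit as soon as possible". The investigator then either continues the patient or stops study medication. If medication is stopped, "The present visit will be recorded as Visit 3, the End of Treatment visit", and the next sentence reads: "The patient will be withdrawn from the study and may be treated with other medication (standard treatment"). The patient is scored Treatment Failure. The synopsis (Visit 2) and Protocol 4.1 carry the same rule.

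Protocol 4.1 and 8.2.4 expect everyone at Visit 4 (Day 15–17) except patients withdrawn from the study or who withdrew consent, and both cite 5.3 for that exception. On leaving the study, Protocol 5.3 says: "Patients must be withdrawn from the study if they withdraw consent to participate". It describes the Visit 2 decision for non-improvers as one about stopping study treatment. The Table 1 footnote on these patients (repeated in SAP Appendix 1) also speaks only of stopping treatment.

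On safety, Protocol 7.2.1.1 covers AEs "that occur during the study (i.e., between study enrollment and Visit 4) must be reported and documented". Protocol 7.2.1.4 adds serious events the investigator learns of after the last visit, up to 30 days after the last dose. Protocol 7.2.1.5 requires serious events and related non-serious events to be followed until resolved, chronic or stable. SAP 4.8.2 displays AEs as numbers and percentages of subjects and numbers of events. SAP 4.8.1 calculates duration of study participation.

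**The concern.** The rule ends scheduled safety observation because of how the patient is doing. Read literally, a patient who stops on Day 5 for an adverse event is still expected at Visit 4, because 5.3 calls that stopping treatment. A patient who stops on Day 5 because the infection is not improving is not expected.

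Loss of follow-up tied to outcome can become loss tied to arm. Protocol 2.2 expects both single components to do less well than the combination. Protocol 6.4 raises worsening patients as a special concern because one arm has no antibiotic. If more patients are stopped in that arm, its new non-serious AEs are looked for over a shorter time. Crude percentages would then make it look safer relative to the combination than it is.

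The unclear status is a problem in its own right. Sites reading 8.2.2 and sites reading 5.3 could handle identical patients differently.

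**Working it through.** The plan gives no figure for this point, so there is none to reproduce. The check sets the passages side by side, counts days, and then illustrates the size.

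**1. Status after stopping for no improvement**

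| Place | What it implies |
|---|---|
| Protocol synopsis (Visit 2), 4.1, 8.2.2 | Stopping medication also means withdrawal from the study |
| Protocol 5.3; Table 1 footnote; SAP Appendix 1 | Stopping study treatment; leaving the study is not mentioned |
| Protocol 4.1, 8.2.4 | Withdrawn patients are excepted from Visit 4, citing 5.3 |
| Protocol 7.2.1.1 | AEs are due up to Visit 4, a visit these patients do not have |

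The cross-reference does not close: the Visit 4 exception points to 5.3, and 5.3 contains no withdrawal for non-improvement. Two further passages show that some patients who stop treatment or take rescue medication are expected to remain in the study. Protocol 6.7.1 says: "The following medications will be prohibited during the study (unless the patient has prematurely discontinued study treatment"). Protocol 8.2.4 says: "If patient took rescue medication (see Section 6.7.2) prior to this visit, the ear discharge will not be collected". These last two do not by themselves contradict 8.2.2, as discussed under the objection.

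**2. Scheduled observation lost**

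Inputs: call on Day 3 or 4; clinic visit as soon as possible, with no limit in days; Visit 4 on Day 15–17. A stopping visit on Day 4–6 is an assumption. Days lost = Visit 4 day − stopping day. Share lost = days lost ÷ (Visit 4 day − 1).

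- Stop on Day 4: 15 − 4 = 11 to 17 − 4 = 13 days; 11/14 = 79% to 13/16 = 81%.
- Stop on Day 5: 10 to 12 days; 10/14 = 71% to 12/16 = 75%.
- Stop on Day 6: 9 to 11 days; 9/14 = 64% to 11/16 = 69%.

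The passive window for serious events stays open. With a last dose on Day 3–6, adding 30 days gives Day 33–36.

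**3. Illustration of the effect on the AE comparison**

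Assumptions, none from the documents: 16 days of follow-up for completers and 5 days for stopped patients; the same constant daily AE rate in both arms; 5% stopped on the combination; 20–40% stopped on fluocinolone alone. Mean follow-up = f × 5 + (1 − f) × 16, where f is the fraction stopped.

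- Combination: 0.05 × 5 + 0.95 × 16 = 15.45 days.
- Fluocinolone, 20% stopped: 0.20 × 5 + 0.80 × 16 = 13.8 days; 13.8/15.45 = 0.89, about 11% fewer AEs observed.
- Fluocinolone, 40% stopped: 0.40 × 5 + 0.60 × 16 = 11.6 days; 11.6/15.45 = 0.75, about 25% fewer.

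A second version works in patient percentages. Assume a true AE risk of 10% over 15 days, a constant hazard, and 4 days for stopped patients. The risk over 4 days is 1 − 0.9^(4/15) = 2.8%. The observed percentage is (1 − f) × 10% + f × 2.8%: about 8.6% at f = 20% and 7.1% at f = 40%.

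**4. Consistency with the stated completion rate**

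Protocol 5.4 expects about 80% to complete, so about 20% not to. If ciprofloxacin alone also had 5% stopped, 2:2:1 allocation would give 0.4 × 5% + 0.4 × 5% + 0.2 × 20% = 8% stopped overall, or 12% with 40% on fluocinolone. The scenario fits within the stated 20%, but that figure says nothing about the split by arm.

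**The case against.** The strongest reply is that much of this is deliberate and harmless.

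- **Follow-up does not stop.** AEs are recorded at the stopping visit (Protocol 8.2.3), and 7.2.1.4 and 7.2.1.5 continue to apply. A reader might infer that safety follow-up ends altogether; the documents do not support that. What is lost is scheduled assessment, new non-serious AEs, and serious events the site never hears about.
- **The expected local events are not AEs.** Protocol 7.2.1.1 counts worsening otalgia, edema or otorrhea as treatment failure, and does not count new disease in the other ear as an AE. This stands: the loss concerns other events.
- **The passages can be read together.** Section 5.3 does not say that consent is the only ground for withdrawal. Protocol 4.1 and 8.2.4 list withdrawn patients separately from those who withdrew consent. Rescue can begin between Visits 3 and 4, so the culture rule in 8.2.4 is coherent. The exemption in 6.7.1 fits patients who stop for other reasons. The per-protocol definitions (Protocol 10.1.4, SAP 4.4) excuse clinical failures from Visit 4, so early exit may be intended. This weakens the evidence from 6.7.1 and 8.2.4. It does not explain why 5.3 and the Table 1 footnote describe the same step without withdrawal, or when the AE period ends for these patients.
- **The bias is assumed.** No stopping rate by arm is given, and the investigator may choose to continue the patient. Dosing lasts 7 days, so a constant daily rate to Day 16 is generous; if events cluster early, the loss is smaller. This stands.
- **Longer follow-up brings its own noise.** The SAP's treatment-emergent definition has no end date, so events arising on later medication would be counted. This stands and is addressed in the fix.
- **The imbalance would be visible.** The SAP summarises treatment duration and reasons for discontinuation by arm, and safety is not formally tested (SAP 4.7.1.2). True, but seeing unequal follow-up does not recover the events missed.

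**Conclusion.** The point holds as a gap in data collection and an inconsistency in patient status. Under 8.2.2, scheduled safety assessment ends at the stopping visit for patients withdrawn for no improvement. If that visit falls on Day 4–6, then 9–13 days of scheduled observation are lost, or 64–81% of the span to Visit 4. Because the loss follows outcome, new non-serious AEs could be under-counted unequally by arm, and the SAP's AE summaries make no adjustment for time observed.

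The 11–25% shortfall is illustrative. It depends on assumed stopping rates, assumed follow-up times and a constant AE rate. A reader might infer that AEs in the fluocinolone arm will be under-counted by this much; the documents show only that it is possible and in which direction.

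A reader might also infer that Visit 4 efficacy is compromised. It is essentially unaffected. These patients are recorded as Treatment Failure, and the SAP scores rescue before Visit 4 and missing efficacy data as failure (4.7.1.1, 4.7.2, 4.7.3). The primary endpoint is assessed at Visit 3.

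**What to change.** Two changes, both about status and data collection.

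1. Reconcile the synopsis (Visit 2), Protocol 4.1 and 8.2.2 with 5.3, 7.2.1.1, the Table 1 footnote and 8.2.4, so that they agree on whether stopping study medication also ends study participation. Correct the Visit 4 cross-reference to 5.3 accordingly.
2. State that, unless consent is withdrawn, AE and concomitant-medication data are collected for these patients through Day 15–17, at the already scheduled Visit 4 or by telephone. In the SAP, make AEs that arise on subsequent medication identifiable in the summaries, so they are not read as effects of the assigned arm.

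The Treatment Failure scoring, the decision to stop and the treatment that follows are unchanged; no view is taken on them here.

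The cost is a wording amendment in a few places, a short SAP addition and some extra site contact. Some patients will decline, so follow-up will not be complete, and some added AEs will relate to later treatment.
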